Arrest of caries lesions will be determined by assessing clinical hardness, colour change, and size of lesions at baseline, at second visit, and at the final study visit. Children will be recruited and we will perform block randomization by site in order to achieve equal proportions in each regimen by clinic site of recruitment. Study visits will occur at the Children's Hospital Research Institute of Manitoba (CHRIM) or at community-based dental clinics. Following informed consent the child's parent/caregiver will complete a short questionnaire (via interview) on general and dental health, oral hygiene, dietary intake of sugars, and family demographics along with the ECOHIS to assess OHRQL. SDF will be applied on the day of recruitment to cavitated lesions involving dentin followed by 5% NaFV. Depending on which frequency regimen children are randomized to, they will return for a second visit. During this second visit, caries lesions treated with SDF at baseline will be assessed to see if caries is arrested as determined through measures of hardness, colour change, and size. At this same visit a second application of SDF will be applied to these initially treated caries lesions followed by 5% NaFV. Children and parents will return for the third and final study visit according to the schedule of their randomized grouping. Parents/caregivers will complete a follow-up questionnaire similar to the

baseline tool. Caries lesions previously treated by SDF will be assessed for clinical hardness, colour change and size to determine if they have arrested.

Population: As ECC is age specific, participants will be < 72 months of age with active caries and their parents/caregivers. The majority will be recruited from community-based dental clinics in Winnipeg (i.e., Access Downtown, Mount Carmel Clinic, and SMILE Plus Children's Dental Clinic) or who are currently on a wait list for dental surgery under general anesthesia in Winnipeg. We found that these were ideal sites for our recently completed feasibility trial of SDF. We will restrict participation to children living in the Winnipeg region or within a one hour drive of Winnipeg to minimize the risk of loss-to-follow-up. Eligibility criteria are designed to select young children who have active caries, and thus are at an increased risk of morbidity from existing caries and onset of new caries.

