Sample and Justification of Sample Size: Sample size for this pilot study has been determined in discussion with [name] (collaborator, Professor & Biostatistician). Our intent is to compare arrest rates between groups and to see whether the three different regimens will yield arrest rates within a range of what we will determine to be clinically acceptable. Based on our recent pilot feasibility study of SDF with 40 children (with 239 lesions) we reported an arrest rate of approximately 96% following two applications of SDF. Results from a recent systematic review state that 80% of lesions can arrest because of SDF. We believe that a range of arrest rates from 80% to 96% yield similar beneficial outcomes in the clinical setting. Based on our pilot study, 40 children had 239 lesions (average 6 lesions/child). With our pilot sample of 239 lesions, it is possible to estimate an arrest rate with a 95% confidence interval to be accurate within $\pm 6.5\%$. With 400 lesions anticipated in our proposed recruitment sample, the 95% confidence interval for the arrest rate would be $\pm 5.0\%$. We propose three SDF regimen groups and anticipate that each group will have 22 children anticipating an average of six lesions. This would mean 396 lesions would be followed in this study. We anticipate that with 400 lesions the percent of arrest will be within $\pm 5\%$ if we have 22 children in each group. To deal with potential drop-outs and loss-to-follow-up of up to 20% we will over recruit by into each group and recruit 28 per group. We anticipate that we can successfully recruit 10 children each month.

Instrumentation and Outcome Measures: Baseline and follow-up visit questionnaires will be a modified versions of those used in our SDF pilot feasibility study (developed by [name] [collaborator] in her SDF efficacy study). The questionnaire collects child and family

demographic information, oral hygiene and use of toothpaste, dietary habits (i.e., snack foods and drinks), consumption of fluoridated water, appearance of the teeth, and symptoms (e.g., pain). The tools also include sections for the parent/caregiver to complete with their child on how the child believes their teeth look and feel and how they rated their visit and SDF treatment.

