Our research staff will contact interested parents/caregivers and will inform them of the study objectives, eligibility criteria, and procedures. Children will undergo a dental screening by the principle investigator or a calibrated and trained dental examiner to determine whether children meet the clinical criteria for this study by having cavitated caries lesions involving dentin (i.e. ICDAS category 5 or 6). Since ECC is more common in disadvantaged populations, we will arrange for transportation (i.e., taxis) for participants. We also anticipate that some participants will be newcomers and will require interpreters. We will arrange for WRHA interpreters when needed. Visits will occur at the principle investigator's dental suite at CHRIM or at one of the community-based clinics.

Baseline visit: Following written informed consent, children will be randomly allocated into one of three groups using sealed envelopes to ensure random allocation. Parents/caregivers will complete the baseline questionnaire administered by interviewer. Children will undergo a dental examination (without x-rays) to record the number of teeth and tooth surfaces with caries meeting ICDAS 5 or 6 criteria and the specific tooth numbers. We will record the location, size, hardness, colour, and activity status of each eligible caries lesion. We will also assess the total number of primary teeth and tooth surfaces affected by caries (i.e., dmft and dmfs). We will also determine the PUFA index. SDF will then be applied with a microbrush for one minute to each cavitated lesion meeting the eligibility criteria followed by 5% NaFV.

Second visit: Depending on the regimen children will return 4 months (Regimen 1), 6 months (Regimen 2), or 1 month (Regimen 3) later for their first follow-up visit and second application of SDF. Parents/caregivers will complete the ECOHIS tool. Prior to the second application of SDF, caries lesions that received the first application of SDF will be assessed to determine if caries is arresting. Lesions will be assessed for colour change, size, and hardness. Clinical data will be recorded including dmft, dmfs, and PUFA scores will be recorded. Following the dental assessment of the lesions under investigation, SDF will be applied to these lesions for one minute followed by 5% NaFV.

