Third visit: Depending on the regimen children will return 4 months (Regimen 1), 6 months (Regimen 2), or 1 month (Regimen 3) later for their final follow-up visit. Parents/caregivers will complete a follow-up questionnaire administered by interviewer. Caries lesions that were treated with applications of SDF will be assessed to see if caries is arrested. Caries lesions will be assessed for colour change, size, and clinical hardness. We will also record dmft, dmfs, and PUFA scores. Clinical data will be recorded on the Clinical Record Form.

Clinical data from baseline and each follow-up visit will be linked with questionnaire data. Data will be entered into a REDCap database and saved on the secure server at CHRIM.

Oral Microbiome Sub-Study: SDF may inactivate cariogenic bacteria in vitro. There was only one study that conducted RNA analysis of plaque in six children before and after treatment (3 receiving SDF and 3 placebo) reporting no changes in relative abundance of cariogenic bacteria. In that study, not only was sample size a major limitation, but the lead author is a director of Advantage Arrest™. Our proposal to assess 30 children would provide statistical power and help elucidate if SDF leads to changes in the oral bacteriome and mycobiome. This will provide novel insights into SDF's mechanism of action, whether antimicrobial, remineralization, or both. Ten children from each regimen will have plaque samples collected. Samples will be obtained at baseline (prior to SDF application), at the first follow-up visit (prior to SDF application), and at the final visit. Nucleic acid isolation from plaque samples will be done using the DNeasy

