An application will be submitted to the University of Manitoba’s Biomedical Research Ethics Board by the June 2019. Additional approvals are being sought from the WHRA and Mount Carmel Clinic. Considering some participants will be First Nations, we will notify Nanaandawewigamig before starting this RCT, although First Nations status will not be a covariate in our data analysis. Written informed consent will be obtained from parents or legal guardians of the child. The consent form will state that parents/caregivers are free to withdraw at any time, without any effect on the child’s dental treatment at the dental clinic they attend. Patients of the PI are eligible to participate. However, he will not obtain consent from parents/caregivers of his own patients. At the end of this RCT we will offer SDF to parents to manage any new caries lesions that have developed on their child’s other teeth or surfaces or those lesions not eligible in this RCT (i.e., ICDAS 3 and 4).

Knowledge Translation (KT):

Study outcomes will be disseminated at conferences and in publications. [name] is a Canadian Institute for Health Research Embedded Clinician Researcher and is integrated into

the Winnipeg Regional Health Authority and Shared Health, providing opportunity to share findings with stakeholders responsible for oral health policy and programs. We will also work with our knowledge users (Drs. [name], [name], and [name]). We will rely on established networks to share our findings. [name] co-leads (and [name] is a member of) the Healthy Smile Happy Child initiative, which promotes early childhood oral health in Manitoba. Telehealth and Zoom conferencing are used for these activities. Drs. [name] and [name] are part of Nanaadawewigamig's Canadian Institutes for Health Research Partners for Engagement and Knowledge Exchange, which will disseminate evidence to communities. [name] also leads the Oral Health and the Aboriginal Child Knowledge Transfer website where findings will be disseminated (> 35,500 page views). The Canadian Dental Association's Knowledge Networks will assist with knowledge translation to inform dental professionals, stakeholders, researchers, and the public. [name] is strategically positioned as chair of the Canadian Dental Association's Committee on Clinical and Scientific Affairs, which provides another avenue to disseminate findings to inform policy and clinical guidelines on SDF.

Significance and Future Directions:

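### Envelope allocation comes before the baseline lesion record, and site blocks with visible regimens leave later allocations partly guessable

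*Combined protocol and SAP*

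**What the plan says.** - **Order of steps (Implementation, Baseline visit).** Once written consent has been given, "children will be randomly allocated into one of three groups using sealed envelopes to ensure random allocation". The paragraph then lists the parent questionnaire, next the dental examination that records location, size, hardness, colour and activity for each eligible lesion, and last the SDF application.
- **Blocking (Methods, Design).** "we will perform block randomization by site in order to achieve equal proportions in each regimen by clinic site of recruitment".
- **Numbers (Sample and Justification of Sample Size).** "each group will have 22 children anticipating an average of six lesions"; to cover losses, "we will over recruit by into each group and recruit 28 per group".
- **Recruitment.** The Population section draws most children from three named community clinics or the surgery wait list. Under Implementation, research staff visit the clinics regularly to recruit, and the investigator or a trained examiner screens for eligibility.
- **Visibility.** The second visit falls at 4, 6 or 1 month according to regimen. No blinding is described.
- **Safeguards.** Allocation follows written consent. The Ethics section says "Patients of the PI are eligible to participate", and adds that the investigator will not take consent from the parents of those patients.
- **Data system (Third visit).** "Data will be entered into a REDCap database".

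The documents do not give the block size or say whether it varies. Nor do they say whether the envelopes are opaque and numbered, or who prepares, holds and opens them.

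**The concern.** There are two separate routes to bias.

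The first needs no guessing. If the envelope is opened before the examination, whoever decides which lesions are eligible, and rates their hardness, colour and size, may already know the regimen. The arrest rate is defined as teeth arrested over teeth treated, so the choice of lesions sets the denominator of the primary outcome. The baseline scores are also the reference for later change.

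The second is prediction. Balanced blocks within a site, combined with past allocations that can be read from return dates, tell recruiters something about the next allocation. Referral, approach, screening and order of enrolment all precede consent, so opening the envelope after consent does not protect them.

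The planned comparison between regimens is a chi-squared test with no baseline adjustment. Adjustment would in any case not reach unmeasured differences between the children enrolled.

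**Working it through.** **1. The plan's own figures.** Allowing for "potential drop-outs and loss-to-follow-up of up to 20" per cent: 22/(1 − 0.20) = 27.5, rounded up to 28 per group, as stated. Total 3 × 28 = 84. The point below does not change this.

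**2. Order of events.** As listed: screening of the child, consent, envelope, questionnaire, lesion examination and scoring, SDF. Screening settles whether the child qualifies. The lesion-by-lesion record that feeds the outcome comes after the envelope.

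**3. Predictability when the block size is known.** Inputs: three regimens in equal ratio (from the documents); a recruiter who sees all earlier allocations at the site and knows the block size (assumptions). The best guess is the regimen with most places left in the block, and it is correct with probability (largest number left)/(places left).

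- Block of 3: (1/3 + 1/2 + 1)/3 = 61.1%. Only the last place is certain: 1/3 = 33.3%.
- Block of 6, by place: 1/3, 2/5, 1/2, 8/15, 3/5, 1. The sum is 101/30, and 101/30 ÷ 6 = 56.1%. The last place is always certain and the fifth is certain with probability 1/5, so 1.2/6 = 20.0%.
- Blocks of 9 and 12: the same recursion, run by exact enumeration.

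| Block size | Guessed correctly | Known with certainty | At least one regimen ruled out |
|---|---|---|---|
| 3 | 61.1% | 33.3% | 66.7% |
| 6 | 56.1% | 20.0% | 46.7% |
| 9 | 53.2% | 14.3% | 35.7% |
| 12 | 51.2% | 11.1% | 28.9% |
| Chance | 33.3% | 0% | 0% |

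**4. Predictability when the block size is not known.** The recruiter guesses the regimen least used so far at the site. The simulation used 5,000 runs and sites of 84/4 = 21 children (an even split over four sources is an assumption).

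| Blocks | Guessed correctly |
|---|---|
| 3 | 61% |
| 6 | 54% |
| 9 | 51% |
| 3 and 6, varied | 57% |
| 6 and 9, varied | 53% |
| 3, 6 and 9, varied | 54% |

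Hiding and varying the block size takes away most of the certainty, but little of the guessing. Varied 3/6/9 blocks do no better on this measure than fixed blocks of 6, because the blocks of 3 pull the figure up.

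**The case against.** Several counter-arguments have force.

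- **Envelopes are not what makes the sequence guessable.** That is correct. The cause is site blocking with visible past allocations, and the same list released from a database would be just as guessable. Envelopes add a different weakness, opening early or out of order, against which no safeguard is described.
- **The motive is weak.** Every child receives SDF on the first day and again later, each regimen follows a published or local recommendation, and the hypothesis is similar arrest rates. Taxis and the one-hour travel limit also reduce selection by distance. This lowers the likelihood of selection; it does not close either route.
- **The investigator does not take consent from own patients.** This is a real safeguard for consent. It does not cover screening, approach or lesion scoring.
- **The listed order may not be the working order.** This is possible, but the text gives only that order and no rule that the examination comes first.

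A reader might infer that the equal-proportions aim forces small blocks. The documents give no block size, and larger blocks could also balance a site of about 21.

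A reader might also put a size on the resulting bias. If severity is assumed to shift by s whenever Regimen 2 looks more or less likely than one third, blocks of 3 give Regimen 2 a mean of (0 + s + s)/3 = 2s/3 and the others (−2s − s + s)/6 = −s/3. The imbalance is then s, which is the assumption itself. Such a figure says nothing about what would happen in this trial.

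**Conclusion.** The point holds as a weakness of procedure. On the stated order, the regimen can be known while lesions are selected and scored at baseline; this rests on the text alone. Guessing above chance is also possible: 51% to 61% for blocks of 12 down to 3 if recruiters know the block size and see past allocations, against 33%. The range is conditional because neither the block size nor the custody of the envelopes is stated, and the visibility of the regimen is inferred from the visit schedule and the absence of any blinding.

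The documents do not support the stronger reading that enrolment will in fact follow the next regimen, or that the comparison will be biased by a given amount. Selection is a risk here, not a finding. The change is still worth making: it is cheap and cannot be made once children are enrolled.

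**What to change.** Replace the envelopes with allocation released from the REDCap database:

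1. The collaborating biostatistician generates and holds the list, stratified by site. Block sizes vary, are not disclosed to recruiters or examiners, and exclude blocks of 3 (for example 6 and 9).
2. The database releases an allocation only after consent, eligibility and the baseline lesion record (location, size, hardness, colour, activity) have been entered and locked for that child.
3. The Baseline visit section is reworded so that the examination precedes allocation.

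Every child receives the same SDF application at this visit, so the later release delays no treatment. It can still come before plaque sampling, which the sub-study needs for ten children per regimen.

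The cost is one set-up and a few protocol sentences, with no change to the 28 per group. The clinics need a connection. Site balance may be slightly looser: an unfinished block can leave two regimens apart by up to 3 children with blocks of 9, against 1 with blocks of 3. About 53% of allocations remain guessable with varied blocks of 6 and 9, so steps 2 and 3 carry most of the benefit.

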The Early Childhood Oral Health Impact Scale (ECOHIS) will be used to assess changes in OHRQL from baseline to completion of study. ECOHIS is a validated tool for use with parents/caregivers of children < 72 months of age. It consists of 13 questions grouped into two sections: 1) child impact, and 2) family impact. The child impact section includes nine questions in four areas: 1) symptoms, 2) functions, 3) psychology, and 4) self-image and social interaction. The family impact component covers two areas: 1) parental distress and 2) family function. Each question is scored from 0 to 5 [0= never, 1= hardly ever, 2= occasionally, 3 = often, 4= very often, 5= don't know]. A total score for each child is calculated by summing up response codes. The ECOHIS will allow us to calculate and compare mean ECOHIS scores at each visit and between groups. Our team has experience with analyzing ECOHIS.

Clinical outcomes assessed will include the proportion of teeth arrested (i.e., "arrest rate" = total number teeth arrested / total number of teeth treated), the proportion of children with any arrested caries, associated morbidity (dental pain and, dental abscess assessed using the PUFA index), and proportion of children requiring dental surgery under GA. The PUFA index is a score of the consequences of severely decayed teeth with visible pulpal involvement (P/p), ulceration caused by dislocated tooth fragments (U/u), fistula (F/f) and abscess (A/a). We will also record dmft and dmfs scores for each child at baseline and at subsequent study visits. The dmft and dmfs scores are cumulative counts of the total number of primary teeth or surfaces decayed, missing due to, or filled because of caries.

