PowerSoil Kit (Qiagen). It allows the isolation of genomic DNA (gDNA) from fungi and Gram (+-) bacteria, which will be used for downstream analyses. For the 16S rRNA (bacteriome) and ITS1 rRNA (mycobiome) amplicon sequencing, isolated gDNA will be used for PCR amplification of the V4 region of the bacterial 16S rRNA gene, and for PCR amplification of the fungal Internal Transcribe Spacer 1 (ITS1) rRNA gene. gDNA will be sequenced at Génome Québec using paired-end Illumina MiSeq PE250 sequencing. Data analysis will be performed in the [name] lab using established methods. Briefly, demultiplexed raw sequencing results will be filtered and clustered into operational taxonomic units (OTUs) and alpha and beta diversity analyses performed using QIIME2 (Quantitative Insights into Microbial Ecology) v. 2018.11. 16S sequences will be aligned and taxonomy assigned with the HOMD database. ITS1 sequences will be aligned and taxonomy assigned with the UNITE database.

Data Analysis:

This study will estimate the success of different SDF. Descriptive statistics will be used (e.g. frequencies, proportions, and means \pm standard Deviations). The “arrest rate” (primary outcome) will be calculated for the second visit and again at the third and final visit. Bivariate analyses will assess changes in clinical measures and survey data from baseline to the follow-up. McNemar’s test will be used to compare the arrest rate between the second and third clinical visits and to compare dichotomous data from the baseline questionnaire with that from the follow-up questionnaire within each regimen. Chi-squared analysis will compare arrest rates between the regimen groups. Paired t-test will be used to compare normally distributed interval data from the baseline questionnaire with that from the follow-up questionnaire within regimens (Mann-Whitney test if not normally distributed). We will rely on repeated measures analysis of variance to assess changes in ECOHIS scores and other continuous data over time (i.e. baseline vs. second visit vs. final study visit) within each regimen group and to assess differences between regimen groups. Although this is a pilot RCT, we will explore potential changes in the oral microbiome of those randomized to different regimens. This will provide insights into potential mechanisms of SDF action, whether it has antimicrobial activity and influences the oral microbiome composition. A p value ≤ 0.05 will be significant.

Ethics:

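### Arrest is read at a different time in each regimen (final visit at 8, 12 or 2 months), so the between-regimen test compares whole regimens and cannot speak to application frequency as Hypothesis 1 is worded

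*Combined protocol and SAP*

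**What the plan says.** The document is a combined protocol and SAP.

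- **Hypotheses, item 1** predicts similar arrest rates when two applications are given at different frequencies. The primary objective refers to application regimens.
- **Implementation, Second visit** sets the visit at 4 months after baseline for Regimen 1 and at 6 months for Regimen 2. For the remaining group it says: "1 month (Regimen 3) later for their first follow-up visit and second application of SDF". Lesions are assessed before that second application.
- **Implementation, Third visit**: children "return 4 months (Regimen 1), 6 months (Regimen 2), or 1 month (Regimen 3) later for their final follow-up visit". The Methods text agrees: "Children and parents will return for the third and final study visit according to the schedule of their randomized grouping".
- **Data Analysis**: the arrest rate, which is the primary outcome, "will be calculated for the second visit and again at the third and final visit". Then: "Chi-squared analysis will compare arrest rates between the regimen groups". The visit for that test is not named, nor is the meaning of the contrast.
- **Data Analysis** also applies repeated-measures ANOVA to ECOHIS and to further measures, given as: "continuous data over time (i.e. baseline vs. second visit vs. final study visit) within each regimen group and to assess differences between regimen groups". Instrumentation and Outcome Measures likewise plans to "compare mean ECOHIS scores at each visit and between groups".
- **Sample and Justification of Sample Size** states an intent to compare groups, and treats arrest rates from 80% to 96% as clinically similar.

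**The concern.** Assessment time is set by the regimen. A reader who takes the chi-squared result as the test of Hypothesis 1 will treat it as a statement about application frequency, when one regimen was read at 2 months and another at 12.

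The error can run either way. If arrest is lost over time, the late reading counts against Regimen 2. If arrest builds slowly, the early reading counts against Regimen 3. A true difference can also be hidden, which matters because similarity is what Hypothesis 1 predicts.

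The second visit is the plainest case. The primary outcome is calculated there, and nothing excludes it from the between-regimen test, yet at that point no child has had the second application that distinguishes the regimens.

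**Working it through.** **1. Assessment times.** The interval at the third visit must run from the second visit; counted from baseline, both visits would fall on the same day. The totals from baseline are derived by addition and are nominal, as no visit windows are given.

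| | Regimen 1 | Regimen 2 | Regimen 3 |
|---|---|---|---|
| Second visit, months from baseline | 4 | 6 | 1 |
| Final visit, months from baseline | 4+4 = 8 | 6+6 = 12 | 1+1 = 2 |
| Months since last application, both visits | 4 | 6 | 1 |
| Applications before second-visit reading | 1 | 1 | 1 |
| Applications before final reading | 2 | 2 | 2 |

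**2. Can time be adjusted for at the final visit?** An intercept, two regimen terms and time make 4 parameters on 3 distinct design points. The rows (1,1,0,8), (1,0,1,12) and (1,0,0,2) have rank 3, so regimen and time cannot be separated by a covariate.

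**3. Lesions per regimen.** The plan's count reproduces: 3 × 22 × 6 = 396, so 132 per regimen.

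**4. How large might a timing effect be?** The documents give no time course, so every curve below is an assumption. Efficacy is equal across regimens unless stated. Lesions are taken as independent, 132 per regimen. Rejection is for the Pearson chi-squared test (2 df, 0.05), by exact enumeration of three binomials; it is 4.8% when all three rates are 96%.

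*Loss since the last application*, 0.96 × exp(−r·t) with t = 4, 6, 1:

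| r per month | Regimens 1, 2, 3 (%) | Regimen 3 minus 2 | Rejection |
|---|---|---|---|
| 0.005 | 94.1, 93.2, 95.5 | 2.4 | 10% |
| 0.01 | 92.2, 90.4, 95.0 | 4.6 | 23% |
| 0.02 | 88.6, 85.1, 94.1 | 9.0 | 57% |
| 0.03 | 85.1, 80.2, 93.2 | 13.0 | 83% |

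The last two rows need 96% to be the rate at time zero. If the pilot's 96% was instead read 4 months after application (the documents do not say), r cannot exceed −ln(0.96)/4 = 0.0102.

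*Build-up from the first application*, 0.96 × (1 − exp(−k·t)), with t = 4, 6, 1 at the second visit and 8, 12, 2 at the final visit:

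| k per month | Second visit (%) | Final visit (%) | Final-visit rejection |
|---|---|---|---|
| 1 | 94.2, 95.8, 60.7 | 96.0, 96.0, 83.0 | 98% |
| 2 | 96.0, 96.0, 83.0 | 96.0, 96.0, 94.2 | 10% |
| 3 | 96.0, 96.0, 91.2 | 96.0, 96.0, 95.8 | 5% |

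*Masking.* Suppose Regimen 3 is truly worse at time zero, at 0.96 × exp(−5r). With r = 0.005 it starts at 93.6% (2.4 points lower); with r = 0.01 at 91.3% (4.7 lower). At the final visit Regimens 2 and 3 then read the same, 93.2% or 90.4%, and the test rejects in 6% or 8% of trials.

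**The case against.** **Randomization protects the comparison of regimens.** The primary objective and the Significance section speak of regimens, and the schedule is printed openly. This stands. A reader might infer that the chi-squared test is invalid or that the regimens may not be ranked. The documents do not support that: regimens can be compared as strategies, each at its own end of schedule, if they are labelled so. What remains is that no section defines the contrast this way, and Hypothesis 1 is worded by frequency.

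**The plan's own similarity range barely moves.** Every row of the loss table lies between 80% and 96%, so timing would not change whether a regimen is called acceptable in those scenarios. This stands for that assumption only. Slower build-up could take Regimen 3 lower: with a time constant of 1.5 months it would read 70.7% at the final visit. That too is assumed.

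**The rejection rates prove little.** They run from 5% to 98% with the chosen curve. Lesions also cluster within children: in a beta-binomial simulation (22 children × 6 lesions per regimen, all at 96%), the plain chi-squared test rejected in 9% to 44% of trials over assumed ICCs of 0.05 to 0.5, with no timing effect at all. The masking result is partly low power: with the same true deficit read at a common 6 months after application, the test rejects in only 10% to 20%. These objections stand, so the point rests on the schedule and not on these figures.

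**The second-visit data are useful.** They give a randomized picture of arrest 1, 4 and 6 months after one application. This stands as a descriptive use, though it need not carry over to two applications.

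**It is a pilot, and secondary outcomes are peripheral.** Both stand. The outcome list includes "dental abscess assessed using the PUFA index), and proportion of children requiring dental surgery under GA", but Data Analysis names no between-regimen test of surgery under general anaesthesia, so a reader should not infer a biased test there.

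**Conclusion.** The concern holds in a limited form. Assessment time is fixed by regimen at both visits. A between-regimen contrast of arrest at the second visit reflects timing and chance only. The final-visit contrast is a valid comparison of whole regimens, but neither a difference nor a similarity in it can be attributed to application frequency. That conclusion follows from the printed schedule and needs no assumption.

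The size and direction of any timing effect are unknown. The 2.4 to 4.6 point gap for 0.5% to 1% monthly loss is an illustration, resting on an assumed 96% at time zero; its rejection rates also assume independent lesions. Each regimen's own arrest rate, read against 80% to 96% with its assessment time stated, is unaffected.

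This should be fixed, because following the plan as worded invites a wrong conclusion on Hypothesis 1. A reader might infer that the visits must be realigned; that goes too far for a pilot in which wording and analysis changes remove the problem.

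**What to change.** 1. In Data Analysis, name the final visit for the between-regimen chi-squared test. Do not compare regimens on second-visit arrest; show it descriptively as arrest 1, 4 and 6 months after one application.
2. Define the final-visit contrast as one of whole regimens, each at its own end of schedule. Report every final arrest rate with its time from baseline (8, 12, 2 months for Regimens 1, 2, 3) and since the last application (4, 6, 1 months), against the 80% to 96% range.
3. Reword Hypothesis 1 and the planned conclusion to match. Regimens may be compared as labelled strategies; no difference or similarity is attributed to application frequency.
4. Do not present the ANOVA contrast between regimens by visit order as a same-time comparison, since the visits fall at 0/4/8, 0/6/12 and 0/1/2 months.

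These changes cost almost nothing and leave all visits and application dates as they are. The price is a narrower between-regimen conclusion.

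Aligning the final assessment is not part of the required fix and is for the sponsor to weigh. A common 12 months from baseline would add 4 months of follow-up in Regimen 1 and 10 in Regimen 3, and would leave 8, 6 and 11 months since the last application. Under 0.5% to 1% monthly loss a 2.3 to 4.4 point gap would remain, now against Regimen 3. The two clocks cannot both be equalized.
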